## **7. INVESTIGATIONAL PLAN**

### **7.1. Overall Study Design**

This is an open-label phase 2 study designed to evaluate the safety and efficacy of ATI-50002 Topical Solution, 0.46% in male and female subjects with androgenetic alopecia. Subjects will be required to apply ATI-50002 study medication to their scalp twice a day for a total of 26 weeks. Subjects will have the option to consent to remain on study for an additional 26 weeks after Visit 10 is completed. All subjects will be required to complete a safety follow up visit 4 weeks after their last application of study medication.

A total of 24 subjects (12 males and 12 females) ages 18-50 years of age with a clinical diagnosis of AGA will be enrolled in the study. Male subjects must have a Norwood Hamilton classification of Type III vertex, IV or V and woman must have a Sinclair Grade of 2, 3 or 4.

Subjects will be required to have a small 1.9 cm diameter circle clipped to ~ 1 mm in length on their balding scalp. Subjects must also agree to have a dot tattoo applied in the center of the clipped area during Visit 2.

Subjects will be required to complete the following treatment visits:

Visit 1: Screening (Day -14-0)

Visit 2: Day 1

Visit 3: Day 21

Visit 4: Day 28

Visit 5: Day 56

Visit 6: Day 84

Visit 7: Day 112

Visit 8: Day 140

Visit 9: Day 168

Visit 10: Day 182

Subjects that consent to remain on study for an additional 6 months of treatment will have the following study visits:

Visit 11: Week 30

Visit 12: Week 35

Visit 13: Week 39

Visit 14: Week 44

Visit 15: Week 48

Visit 16: Week 52

All subjects will be required to have a Follow up Safety Visit 4 weeks post last application of study medication.

All protocol defined treatment assessments are outlined in [Table 2](#) .

## **7.2. Number of Subjects**

A total of 24 evaluable subjects will be enrolled to the study (12 male and 12 female) at approximately 3 investigational centers.

## **7.3. Treatment Assignment**

This is an open label study. All subjects will apply ATI-50002 Topical Solution 0.46% twice a day for 26 weeks followed by a 4 week follow up period.

## **7.4. Criteria for Study Termination**

This study may be terminated prematurely in whole or in part due to a change in the benefit/risk profile for ATI-50002 Topical Solution such that continuation of the study would not be justified on medical or ethical grounds. This determination may be made by the Study Investigators in conjunction with the Sponsor, or by IRB or the U.S. Food and Drug Administration (FDA). The Sponsor may also elect to terminate the study if enrollment is sufficiently slow to prevent the completion of the study in an acceptable timeframe, or if ATI-50002 development is discontinued.

If the study is terminated prematurely, the Sponsor will notify the Study Investigators and the FDA. The Investigator must promptly notify all enrolled subjects and the IRB of study termination.

## 7.5. Schedule of Assessments

**Table 2: Schedule of Assessments-Initial 26 weeks of Treatment**

	Screening	Baseline	Treatment								Follow up Safety/Early Termination Visit 
	Visit 1	Visit 2	Visit 3	Visit 4	Visit 5	Visit 6	Visit 7	Visit 8	Visit 9	Visit 10	
			Week 3	Week 4	Week 8	Week 12	Week 16	Week 20	Week 24	Week 26	4 weeks post last application of ATI-50002
Treatment Day	-14 to 0	1	21	28	56	84	112	140	168	182	
Visit Windows	N/A	N/A	+/- 3 days	+/-4 days	+7 days	+/-7 days	+7 days	+/-7 days	+/-7 days	+7 days	+7 days
Informed Consent 	X										
Inclusion/Exclusion Criteria	X	X									
Demographics and Medical History	X										
Physical Exam 	X										X
Vital Signs 	X	X	X	X	X	X	X	X	X	X	X
Fitzpatrick Skin Type	X										
Prior Hair Treatment Assessment 	X										

	Screening	Baseline	Treatment								Follow up Safety/Early Termination Visit 
	Visit 1	Visit 2	Visit 3	Visit 4	Visit 5	Visit 6	Visit 7	Visit 8	Visit 9	Visit 10	
			Week 3	Week 4	Week 8	Week 12	Week 16	Week 20	Week 24	Week 26	4 weeks post last application of ATI-50002
Treatment Day	-14 to 0	1	21	28	56	84	112	140	168	182	
Visit Windows	N/A	N/A	+/- 3 days	+/-4 days	+7 days	+/-7 days	+7 days	+/-7 days	+/-7 days	+7 days	+7 days
Clinical Chemistry and CBC 	X				X		X		X	X	X
Quantiferon Gold 	X										
Total Iron Binding Capacity (TBIC), Serum Iron, Serum Ferritin	X										
Dihydrotestosterone (DHT), Testosterone, Estrogen, DHEA	X				X		X		X	X	X
Urine Pregnancy Test		X		X	X	X	X	X	X	X	X
Serum Pregnancy	X										
Serum PSA	X										
Thyroid Panel	X										
ECG	X			X						X	X

	Screening	Baseline	Treatment								Follow up Safety/Early Termination Visit 
	Visit 1	Visit 2	Visit 3	Visit 4	Visit 5	Visit 6	Visit 7	Visit 8	Visit 9	Visit 10	
			Week 3	Week 4	Week 8	Week 12	Week 16	Week 20	Week 24	Week 26	4 weeks post last application of ATI-50002
Treatment Day	-14 to 0	1	21	28	56	84	112	140	168	182	
Visit Windows	N/A	N/A	+/- 3 days	+/-4 days	+7 days	+/-7 days	+7 days	+/-7 days	+/-7 days	+7 days	+7 days
Norwood-Hamilton classification(males); Sinclair Scale (females)Assessment	X	X					X			X	X
Target Area Hair Identification and Tattoo application 		X									
Global Scalp Photograph 	X	X 			X 		X 			X 	X
Macro Scalp Photographs 		X			X		X			X	
Target Area Hair Count (TAHC) and Target Area Hair Width (TAHW) 		X			X		X			X	
Demonstration of study drug application 		X		X	X	X	X	X	X	X 	
Dispensing of study medication 		X		X	X	X	X	X	X	X 	

	Screening	Baseline	Treatment								Follow up Safety/Early Termination Visit 
	Visit 1	Visit 2	Visit 3	Visit 4	Visit 5	Visit 6	Visit 7	Visit 8	Visit 9	Visit 10	
			Week 3	Week 4	Week 8	Week 12	Week 16	Week 20	Week 24	Week 26	4 weeks post last application of ATI-50002
Treatment Day	-14 to 0	1	21	28	56	84	112	140	168	182	
Visit Windows	N/A	N/A	+/- 3 days	+/-4 days	+7 days	+/-7 days	+7 days	+/-7 days	+/-7 days	+7 days	+7 days
Investigator Assessment of Hair Growth					X		X			X	
Subject Self - Assessment of Hair Growth					X		X			X	
Local Skin Reaction Assessment		X	X	X	X	X	X	X	X	X	X
Adverse Events 							X				
Concomitant Therapies							X				

A written, signed ICF must be obtained from each subject prior to performing any study related procedure

 A physical exam includes: general appearance, examination of head, eyes, ears, nose and throat, respiratory, cardiovascular, abdominal, neurological, musculoskeletal, lymphatic and skin assessment.

Vital signs include: oral or ear temperature, blood pressure, heart rate, respiration rate (height and weight at baseline only).

 Prior therapies or treatments a subject received to treat his/her AGA must be documented for each subject.

 Serum chemistry panel to include: albumin, alk phos, ALT, AST, BUN, bicarbonate, calcium, chloride, creatinine, glucose, lactate dehydrogenase (LDH), phosphorus, potassium, sodium, total bilirubin, total protein, uric acid, total cholesterol, LDL, HDL triglycerides, CPK, and complete blood count including differential.

 All subjects must have a blood sample drawn to test for the tuberculosis virus. The blood sample will be sent to a central laboratory for analysis and results must be received prior to enrolling the subject.

 The investigational study staff will be required to identify target area of the scalp that is located in an actively balding area. Directions for proper hair clipping are outlined in Section 9.2. Sites will be required to apply a permanent dot tattoo to the subject’s scalp to identify the target hair area.

Global scalp photographs are to be performed at the screening visit. If the photos are not of the appropriate quality, the site staff will perform a re-shoot at Visit 2.

 Canfield staff will review all global photographs within 2 days of the photographs being submitted. If a re-take is required, Canfield will notify the site and the re-take photographs will need to be performed within 7 days of the visit.

 Canfield staff will review all macro photographs within 2 days of the photographs being submitted. If a re-take is required, Canfield will notify the site and the re-take photographs will need to be performed within 7 days of the visit.

Sites will take the macro photographs and transmit these to Canfield in order for the Canfield scientists to perform the Target Area Hair Counts and the Target Area Hair Widths. The TAHC and TAHW will be entered into the Canfield database.

Sites will be required to review with each subject the proper application of the study medication and remind the subjects that they are only to wash their hair with the same shampoo/conditioner and maintain the same hair style throughout the study.

Subjects will be dispensed bottles of study medication at each monthly visit. Study medication will be weighed prior to dispensing the medication to the subject and upon return of both used and unused bottles.

 Subjects that are not remaining on protocol therapy for an additional 6 months of treatment will not have study medication dispensed at Visit 10.

All non-serious AEs will be collected from the time of first study medication application until the final study visit. Serious AEs will be collected from the time of consent through the final study visit.

 Subjects that consent to remain on study for an additional 6 months of treatment will continue on study with Visit 11 (week 30) and then will have a final follow up Visit 4 weeks after the last application of study medication in the 6-month extension part of the study. Those subjects that do not consent to continuing on study medication for an additional 6 months will be required to have a final safety follow up visit conducted at week 30. For those subjects that discontinue the study early, they must return to the clinic 4 weeks following the last study medication application for a final safety visit.

**Table 3: Schedule of Assessments – 6-month Extension Study**

							Follow up Safety/Early Termination Visit
	Visit 11	Visit 12	Visit 13	Visit 14	Visit 15	Visit 16	Visit 17
Treatment week	Week 30	Week 35	Week 39	Week 44	Week 48	Week 52	Week 56
Visit Windows	+7 days	+7 days	+7 days	+7 days	+/-7 days	+7 days	+7 days
Physical Exam 							X
Vital Signs 	X	X	X	X	X	X	X
Clinical Chemistry and CBC 			X	X		X	X

Dihydrotestosterone (DHT), Testosterone, Estrogen, DHEA			X			X	X
Urine Pregnancy Test	X		X	X	X	X	X
ECG			X				X
Norwood-Hamilton classification(males); Sinclair Scale (females)Assessment						X	X
Global Scalp Photograph			X 			X 	X
Macro Scalp Photographs 						X 	
Target Area Hair Count (TAHC) and Target Area Hair Width (TAHW) 						X	
Demonstration of study drug application 	X	X	X	X	X	X	
Dispensing of study medication 	X	X	X	X	X	X	
Investigator Assessment of Hair Growth			X			X	X
Subject Self - Assessment of Hair Growth			X			X	X

Local Skin Reaction Assessment	X	X	X	X	X	X	X
Adverse Events 	X						
Concomitant Therapies	X						

 A physical exam includes: general appearance, examination of head, eyes, ears, nose and throat, respiratory, cardiovascular, abdominal, neurological, musculoskeletal, lymphatic and skin assessment.

 Vital signs include: oral or ear temperature, blood pressure, heart rate, respiration rate.

 Serum chemistry panel to include: albumin, alk phos, ALT, AST, BUN, bicarbonate, calcium, chloride, creatinine, glucose, lactate dehydrogenase (LDH), phosphorus, potassium, sodium, total bilirubin, total protein, uric acid, total cholesterol, LDL, HDL triglycerides, CPK, and complete blood count including differential.

 Canfield staff will review all global photographs within 2 days of the photographs being submitted. If a re-take is required, Canfield will notify the site and the re-take photographs will need to be performed within 7 days of the visit.

 Canfield staff will review all macro photographs within 2 days of the photographs being submitted. If a re-take is required, Canfield will notify the site and the re-take photographs will need to be performed within 7 days of the visit.

 Sites will take the macro photographs and transmit these to Canfield in order for the Canfield scientists to perform the Target Area Hair Counts and the Target Area Hair Widths. The TAHC and TAHW will be entered into the Canfield database.

 Sites will be required to review with each subject the proper application of the study medication and remind the subjects that they are only to wash their hair with the same shampoo/conditioner and maintain the same hair style throughout the study.

 Subjects will be dispensed bottles of study medication at each monthly visit. Study medication will be weighed prior to dispensing the medication to the subject and upon return of both used and unused bottles.

 All non-serious AEs will be collected from the time of first study medication application until the final study visit. Serious AEs will be collected from the time of consent through the final study visit.

 A final safety follow up visit will be conducted at week 56 (Visit 17). For those subjects that discontinue the study early, they must return to the clinic 4 weeks following the last study medication application for a final safety visit.

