#### **9.5. Application of Study Medication**

Subjects will be instructed to apply a thin film of ATI-50002 Topical Solution 0.46% (up to 4-mL), twice-daily; once in the morning and approximately 12 hours later to the balding area of the clean dry scalp. Refer to [Appendix 1](#) for the complete application instructions. The subject must wash her/his hands thoroughly before and after each study drug application. Investigational site staff will dispense a month's supply of study medication along with disposable droppers to the subject at each study visit. Study medication bottles will be weighed by the site staff at the time of dispensing and when the bottles are returned. Subjects are to return used and unused study medication at each study visit. The disposable droppers should be disposed of at the subject's home.

At each study visit, the study staff will review the study medication instructions and proper application technique. ([Appendix 1](#)) with the subject. During Visit 2, the subject will apply the first dose of study medication in the office under the instruction and supervision of the study staff.

During each site visit, the study staff member will:

- Dispense study medication bottles to the subject.
- Instruct the subject on the appropriate application technique following instructions in [Appendix 1](#).
- Weigh the bottles prior to dispensing the study medication
- Observe the subject's first study medication application to ensure proper coverage and monitor the subject for at least 20 minutes (Visit 2 only).

All used study medication bottles will be weighed by the investigational site at each visit.

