**Table 5: Investigational Product**

STUDY MEDICATION INFORMATION	
Study medication name	ATI-50002
Dosage Strength	0.46%
Manufacturer	PMRS, Inc., Horsham, PA
Pharmaceutical Form	Topical Solution
Container	Amber Glass Bottle, 120 mL with screw cap
Storage Conditions	59°F to 77°F (15°C to 25°C)
Dose regimen	
Route	Topical
Frequency	Twice-daily
Duration of administration	52 weeks
Other supplies	Disposable, single-use droppers will be provided.

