#### **12.1.5. Pregnancy Tests**

Subjects who are WOCBP must have a negative serum pregnancy test result at Screening (Visit 1) to continue in the study, and a negative UPT at Baseline (Visit 2) prior to study entry. If the result of any post-treatment urine pregnancy test is positive, the subject will be withdrawn from the study and the subject’s pregnancy documented and followed. In addition, the investigator or designee will perform a urine pregnancy test for subjects who are WOCBP at monthly visits during the study.

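### The extension schedule (Table 3) dispenses study drug at Week 52, when treatment ends, and omits the urine pregnancy test at Week 35, when drug is dispensed

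*Protocol*

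**What the plan says.** **End of treatment.** Protocol Section 7.1 sets 26 weeks of treatment and adds: "Subjects will have the option to consent to remain on study for an additional 26 weeks after Visit 10 is completed". In Table 5 the row "Duration of administration" reads 52 weeks. Table 2 footnote 15 gives extension subjects "a final follow up Visit 4 weeks after the last application of study medication in the 6-month extension part of the study", and Table 3 footnote 10 places that visit at Week 56 (Visit 17).

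**Dispensing.** In Table 3 the demonstration row and the row "Dispensing of study medication 8" (the 8 is a footnote marker) are marked at Visits 11 to 16 (Weeks 30, 35, 39, 44, 48 and 52) and blank at Visit 17. Section 9.5 has sites hand out a month's "supply of study medication along with disposable droppers to the subject at each study visit". At the earlier stopping point, Table 2 footnote 14 makes an exception: "Subjects that are not remaining on protocol therapy for an additional 6 months of treatment will not have study medication dispensed at Visit 10". Table 3 has no equivalent for Visit 16.

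**Pregnancy testing.** Section 12.1.5 states that "the investigator or designee will perform a urine pregnancy test for subjects who are WOCBP at monthly visits during the study", and that a positive post-treatment urine test leads to withdrawal. In Table 3 the urine test is marked at Visits 11, 13, 14, 15, 16 and 17. Only Visit 12 is blank.

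**The concern.** The schedule table is what site staff work from, and here it conflicts with the protocol's own text in two places.

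At Visit 16, drug handed out at Week 52 has no planned dosing period. If it is used, one of two things follows. Visit 17 may stay at Week 56, in which case its assessments (physical examination, ECG, chemistry and blood count, hormones, Norwood-Hamilton or Sinclair stage, global photographs with the investigator and subject ratings, local skin reactions) are made on drug or after a shortened off-drug interval. Or the 4-week rule is kept and Visit 17 moves past Week 56. The SAP lists each subject's last application date and computes treatment duration from it, so an overrun would be seen, but only after the exposure had occurred.

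At Visit 12, women of child-bearing potential would be given further drug without the test that Section 12.1.5 uses to trigger withdrawal.

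**Working it through.** The plan gives no figure to reproduce. The check is a comparison of table cells with text rules, plus calendar arithmetic.

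**1. When dosing ends**
- Treatment: 26 + 26 = 52 weeks (Section 7.1), in agreement with Table 5.
- Follow-up: 52 + 4 = Week 56, in agreement with Table 3 footnote 10.
- The month's supply from Visit 15 (Week 48) lasts to 48 + 4 = Week 52. Nothing further is needed at Visit 16.

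**2. Size of a possible overrun**
- Supply, taking the maximum 4 mL twice daily for 28 days: 4 × 2 × 28 = 224 mL, or 224 / 120 = 1.87 bottles of 120 mL.
- If *d* extra days are dosed (0 to 28) and Visit 17 stays at Week 56, the nominal off-drug interval is 28 − *d* days: 28 if the supply is unused, 14 if half is used, 0 if all is used.
- If the 4-week rule is kept and all the supply is used, Visit 17 falls at 56 + 4 = Week 60.
- These are nominal values. Visits 16 and 17 each have a +7-day window, so with a last application at Visit 16 the interval already ranges from 28 − 7 = 21 to 28 + 7 = 35 days without any extra dosing.

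**3. Gaps between pregnancy tests**

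| Period | Scheduled tests | Nominal gaps (days) |
|---|---|---|
| Table 2 | Days 1, 28, 56, 84, 112, 140, 168, 182 | 27, 28, 28, 28, 28, 28, 14 |
| Visit 10 to Visit 11 | Weeks 26, 30 | 28 |
| Table 3 | Weeks 30, 39, 44, 48, 52, 56 | **63**, 35, 28, 28, 28 |

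- Weeks 30 to 39: 9 × 7 = 63 days. Visits 11 and 13 each have a +7-day window, so the range is 63 − 7 = 56 to 63 + 7 = 70 days.
- Scheduled applications in that gap: 63 × 2 = 126.
- Dispensing visits without a urine test: 0 of 8 in Table 2 (Visits 2 and 4 to 10) and 1 of 6 in Table 3 (Visit 12).
- With a test at Visit 12 the gap splits into 35 + 28 days, and no nominal gap on treatment exceeds 35 days.

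**4. Could the blank cell be an extraction fault?** This is unlikely. The pregnancy-test row has all seven cells, and the chemistry row of the same table (Visits 13, 14, 16 and follow-up) agrees with the SAP's laboratory timepoints. The SAP has no pregnancy-test table that would check the cell directly.

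**The case against.** The strongest reply is that these are clerical slips with little practical consequence.

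- *The 52-week limit is clear elsewhere.* This is true. An overrun needs a site to dispense and a subject to keep applying drug, so the effect is conditional.
- *The Visit 16 marks may serve other purposes.* Footnote 8 covers weighing returned bottles, and footnote 7 covers the reminder about shampoo and hair style, which still matters because photographs are taken at Visit 17. This explains the marks in part and is a reason to prefer a footnote over deletion. But the rows are labelled dispensing and demonstration, and nothing limits them at Visit 16.
- *Section 9.5 cannot be read literally*, since the tables mark no dispensing at Visits 1, 3 or 17. This stands, and Section 9.5 is only weak support. The conflict between Table 3 and the 52-week limit does not depend on it.
- *Pregnancy has other safeguards.* Section 12.4.2 requires highly effective contraception and immediate contact if pregnancy is suspected, and Section 12.1.5 already calls for monthly testing. These lower the risk. They do not replace the test, and a site following the table would miss it.
- *The analysis does not change.* This is correct. Hair count and hair width are last measured at Visit 16, and the Visit 17 summaries are descriptive in a single-arm study.

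**Conclusion.** The concern holds on both counts. Table 3 is wrong as written at Visit 16 and at Visit 12, and both entries should be corrected because they instruct sites on drug exposure and on a pregnancy safeguard.

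For Visit 16, the consequence is up to about 4 extra weeks of exposure. It assumes that a month's supply is dispensed and used; if the supply is unused, the off-drug interval remains the planned 28 days. The planned number exposed to this error is 24 subjects, fewer if some do not enter the extension.

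For Visit 12, the consequence is a 63-day gap between tests (56 to 70 with windows). It assumes that sites follow the table rather than the text rule. The planned number is 12 women, fewer if some do not continue or are not of child-bearing potential.

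The figures 24 and 12 are planned enrolment, not firm caps: the synopsis calls them approximate and Section 7.2 refers to evaluable subjects. No efficacy estimate through Visit 16 is affected.

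**What to change.** 1. Add a footnote to the Visit 16 demonstration and dispensing cells of Table 3, parallel to Table 2 footnote 14, stating that no drug is dispensed and that the visit is for return and weighing of bottles, with the hair-care reminder kept. Deleting the two marks would also work, since Section 9.5 still requires used bottles to be weighed at each visit, but the footnote is clearer.
2. Mark the urine pregnancy test at Visit 12 (Week 35).
3. As clean-up only, update the laboratory visit list in Section 12.1.7.1 to match Table 3 and the SAP: Visits 13, 14, 16 and 17, with Week 30 for subjects who do not continue. Sections 12.1.3, 12.1.4 and 12.1.6 also stop at Visit 11 and can be brought into line at the same time.

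The cost is a protocol clarification and one urine test per woman of child-bearing potential at an existing visit. No visits are added and the analysis is unchanged.

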## **8. SELECTION AND WITHDRAWAL OF SUBJECTS**

### **8.1. Subject Inclusion Criteria**

Subjects must meet the following criteria to be eligible for participation in the study:

1. Able to comprehend and willing to sign an Informed Consent Form (ICF).
2. Male subjects and non-pregnant, non-nursing female subjects 18 to 50 years of age with a clinical diagnosis of AGA.
3. Male subjects with a Norwood-Hamilton classified as III vertex, IV or V and woman subjects with a Sinclair Grade 2, 3 or 4.
4. Subjects willing to agree to have small 1.9 cm diameter circle of hair clipped to ~ 1 mm in length on their balding scalp.
5. Subjects willing to agree to have a permanent dot tattoo applied to their scalp to mark the center of the identified target area.
6. Subjects must agree to maintain the same hair style and hair care regimen during the study.
7. Subjects must agree to not use a medicated shampoo or conditioner containing biotin, saw palmetto or tea tree oil (melaleuca oil) throughout the course of protocol treatment and refrain from hair weaving, hair extensions, texturizers, relaxers, occlusive wigs and non-study hair growth products during the study and for a period of 30 days prior to Visit 2.
8. Subjects must have an absolute neutrophil count (ANC)  $>1,000/\text{mm}^3$ , and a platelet count  $>50,000/\text{mL}$ .
9. Male subjects with a serum prostate-specific antigen (PSA) level of  $<2.0 \text{ ng/mL}$ .
10. Subjects receiving oral or topical hormones must be on a stable dose for 6 months prior to Visit 2.
11. Subjects must be willing to refrain from washing hair, using hair products, and participating in strenuous exercise that would cause profuse sweating for 6 hours after each treatment application with ATI-50002.
12. Woman of child bearing potential (WOCBP) must agree to use an approved method of highly effective birth control for the duration of the study and for 30 days after last study medication application.
13. Sexually active male subjects must agree to use a barrier form of birth control from the first application until 30 days post last application of ATI-50002.

